4 ELIGIBILITY

- Subject population: Adolescents and young adults undergoing tonsillectomy
- Inclusion criteria
 - Adolescents and young adults aged 12-25 years will be eligible to be recruited if they undergo palatine tonsillectomy with or without adenoidectomy on the pediatric or general otolaryngology service of the University of Michigan Medical School, and if they are not:
 - Patients in foster care or patients with a legal guardian
 - Patients with developmental delays, such as autism
 - Patients who are non-English speaking
 - Patients with recent suicidal ideation
 - Patients undergoing emergent tonsillectomy

- Exclusion criteria for primary analysis analyzing prescribing
 - Patients who were approached for consent but declined
 - Patients with prescription opioid use prior to surgery
 - Patients undergoing additional major procedures at the same time as tonsillectomy
 - Patients enrolled in another study
 - Patients who are not prescribed opioids post-operatively
 - Patients who are enrolled in the “M-POP” pathway, which includes education about pain management and a small initial opioid prescription (10 doses)
 - Patients with hospitalization with length of stay > 1 day after surgery
- Additional exclusion criteria for secondary analysis examining patient-reported outcomes through surveys
 - Patients who were not reached for consent
 - Patients who do not complete the baseline and post-operative day 14 surveys
- Inclusion of vulnerable populations: The purpose of this study is to evaluate an intervention on opioid prescribing to adolescents and young adults. As such, minors must be included in the study.

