6 STUDY DESIGN AND PROCEDURES

- Study design
 - The study will use a difference-in-differences design in which changes before and after the intervention will be compared between a treatment group and a control group.
 - The treatment group will include all patients undergoing tonsillectomy at C.S. Mott Hospital by a pediatric otolaryngology faculty member at the University of Michigan.
 - The control group will include all patients undergoing tonsillectomy at University Hospital, Brighton Center for Specialty Care, or Livonia Center for Specialty Care by a general otolaryngology faculty member at the University of Michigan.
- Data collection procedures throughout the study
 - There will be three sets of surveys: a baseline survey, daily surveys on post-operative days 1-13, and a final survey on post-operative day 14. Post-operative surveys will be sent to all patients who enroll, including those who are not prescribed opioids post-operatively. These patients will not be included in the primary or secondary analysis but will be analyzed in a separate study examining pain recovery without opioids.
 - Baseline survey: Patients will be asked to complete a 10-15 minute survey assessing demographics, reason for tonsillectomy, current pain, chronic pain, history of opioid use, history of opioid misuse, family chronic opioid use, depression, substance use disorders, anxiety, sleep, and global health. Patients will be e-mailed a link to the baseline survey upon enrollment; for patients who cannot receive e-mail links, the survey will be administered over the phone. For patients at Mott or University Hospital recruited in-person, the baseline survey will be administered by a study team member in-person through Qualtrics on a tablet. Patients sent the baseline survey who do not complete it before surgery will be contacted via e-mail or by phone to remind them or approached in-person to complete it through Qualtrics on a tablet. If patients are contacted by phone, they will be given the option to complete the survey over the phone.

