- Data from the daily surveys will be used to assess whether daily opioid consumption reports matches the consumption reported on the final post-operative day 14, and will also be analyzed in a separate study assessing the trajectory of pain and opioid use after tonsillectomy.
- We will fit linear or logistic regression models assessing outcomes as a function of an indicator of post-intervention status, an indicator of treatment group status, and its interaction, controlling for covariates such as demographics (e.g., age, sex) and baseline co-morbidities (e.g., depression, anxiety). We will graphically and statistically assess the comparability of pre-intervention monthly trends in outcomes between the treatment and control groups.

- We hypothesize that there will be no change in outcomes in the control group (i.e., that the post-intervention trend in outcomes in the control group will be an extension of the pre-intervention trend in outcomes). In contrast, we hypothesize that the number of doses and opioid consumption will drop in the treatment group after the intervention; that the proportion of patients with prescriptions concordant with the new defaults will increase after the intervention; and that there will be no change in balancing measures such as pain control or depression.
- Sensitivity analyses
 - Statistical modeling: we will explore whether results change when replacing the indicator of treatment group status with a vector of fixed effects for the prescribing clinician, and will explore the feasibility of using an interrupted time series approach instead of a difference-in-differences approach.
 - We will determine whether any otolaryngology residents wrote opioid prescriptions for both a pediatric otolaryngology and general otolaryngology patients in the post-intervention period, and exclude data from any such residents from the analysis
 - We will exclude opioid prescriptions written for patients of the chief of pediatric otolaryngology, who will be involved in setting the new defaults
- Subgroup analysis will occur by age group (ages 12-17 years vs 18 and older), gender, payer type (private/public), and baseline co-morbidities (e.g., depression and anxiety).
- We will separately analyze data from pediatric otolaryngology patients undergoing surgery outside of Mott and general otolaryngology patients undergoing surgery at Mott to assess for any spillover effects.

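### Does adjusting for baseline depression and anxiety cut the records-based primary analysis down to survey responders?

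*Combined protocol and SAP*

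**What the plan says.** Section 10 (Statistical considerations) describes linear or logistic models with a post-intervention indicator, a treatment-group indicator and their interaction, "controlling for covariates such as demographics (e.g., age, sex) and baseline co-morbidities (e.g., depression, anxiety". It does not separate the primary from the secondary analysis. The same section lists subgroups that include "payer type (private/public), and baseline co-morbidities (e.g., depression and anxiety", again without assigning them to either analysis. It gives no rule for missing covariates.

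Section 6 names depression and anxiety among the topics of the baseline survey, which goes to people who enroll: "Patients will be e-mailed a link to the baseline survey upon enrollment". Section 11.3 adds that the PHQ-8 is given in the baseline and day 14 surveys. The query of DataDirect and MiChart in section 6 lists prior opioid use, demographics, prescription parameters, return visits and refills. It lists no mental-health diagnosis.

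Section 4 removes "Patients who were approached for consent but declined" from the primary analysis. Two further exclusions apply to the secondary analysis only: "Patients who were not reached for consent" and "Patients who do not complete the baseline and post-operative day 14 surveys". Section 10 expects 198 patients (113 treatment, 85 control) in the primary analysis and, at 65% consent, 129 (74 and 55) in the secondary analysis.

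**The concern.** The primary analysis is meant to cover patients whom the surveys miss. Someone who was never reached for consent has a prescription and refill history in the record but no baseline survey. If the depression and anxiety terms in section 10 are survey scores, that patient has missing covariates. Standard regression software then drops the record unless told otherwise.

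The adjusted prescribing and utilization results would in that case describe only people who took the baseline survey, and the primary population would move close to the secondary one. At stake are coverage and precision. Because the covariate list is open, the choice could also be made after the outcome data are available.

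**Working it through.** **Reproducing the plan's figures.** 113 × 0.65 = 73.45 (plan: 74). 85 × 0.65 = 55.25 (plan: 55). 198 × 0.65 = 128.7 (plan: 129). These agree to rounding. The gap is 198 − 129 = 69 patients: 39 treatment and 30 control.

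**What has to happen for patients to be lost.** Two conditions are needed: survey-measured depression or anxiety enters the primary model, and records with missing values are dropped. Neither is written in the plan.

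**Size if both happen.** Let s be the share of the 69 non-consenters who were not reached; the rest declined and are already excluded by section 4. With p for the primary set, f for the fitted set, and T and C for treatment and control:

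SE ratio = √[(1/fT + 1/fC) / (1/pT + 1/pC)]

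This assumes independent patients, the same pre/post split and outcome distribution in both sets, and covariates that explain no variance. For s = 1 with all 129 having baseline data:

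√[(1/74 + 1/55) / (1/113 + 1/85)] = √(0.03170 / 0.02061) = 1.24

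The documents do not say exactly what 129 counts, so three readings are shown. The 90% completion rates are assumptions.

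| Reading of 129 | s | Primary set | Fitted set | Loss | SE ratio |
|---|---|---|---|---|---|
| All have baseline data | 0 | 129 | 129 | 0 | 1.00 |
| | 0.5 | 163.5 | 129 | 34.5 (21.1%) | 1.126 |
| | 1 | 198 | 129 | 69 (34.8%) | 1.240 |
| Completed both surveys, 90% day 14 completion (129/0.9 = 143.3 with baseline) | 0 | 143.3 | 143.3 | 0 | 1.00 |
| | 0.5 | 170.7 | 143.3 | 27.3 (16.0%) | 1.092 |
| | 1 | 198 | 143.3 | 54.7 (27.6%) | 1.176 |
| Consented, 90% baseline completion (129 × 0.9 = 116.1 with baseline) | 0 | 129 | 116.1 | 12.9 (10.0%) | 1.054 |
| | 0.5 | 163.5 | 116.1 | 47.4 (29.0%) | 1.187 |
| | 1 | 198 | 116.1 | 81.9 (41.4%) | 1.307 |

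The s = 0 rows treat 198 as a count made before decliners are removed. The s = 1 rows are extreme bounds, since they need every non-consenter to have been missed rather than to have refused. Section 5 provides day-of-surgery recruitment at Mott and University Hospital for patients not contacted beforehand.

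The ratios also lean high. Covariates that explain outcome variance offset part of the loss, and so does correlation within prescribers. As an illustration, assume 10 patients per clinician and period, falling to 6.5. The variance of a clinician-period mean is proportional to [1 + (m − 1)ρ]/m. With ρ = 0.05 the SE ratio is √(0.1962/0.1450) = 1.16; with ρ = 0.10 it is √(0.2385/0.1900) = 1.12.

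**Whether the text commits to survey scores.** It does not. Where section 10 means a survey instrument among its outcomes, it names it (PHQ-8, the PROMIS forms). For covariates it speaks only of co-morbidities, by example. Nor is the record query in section 6 a complete list of chart data. Section 4 needs "Patients undergoing additional major procedures at the same time as tonsillectomy" and length of stay for primary-analysis patients who were never surveyed, and it lists "Patients with recent suicidal ideation" among the eligibility bars. None of these is in that query list. The admission history and physical is already read to establish prior opioid use. Taking recorded diagnoses from the chart would therefore comply with the plan.

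**The case for a change.** The strongest argument for a change is that section 10 permits two fits with different primary populations: chart covariates for everyone, or survey covariates for responders. Dropping incomplete records is the usual default when nothing is said, and leaving the choice open allows it to be made with results in view. Missed contact may also differ between groups. Section 5 gives Brighton and Livonia patients, all controls, telephone recruitment only, while Mott and University Hospital have the in-person fallback. A few sentences would close the gap.

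It is true that the covariates are not listed by analysis and that no missing-covariate rule is given. The difference in recruitment route is also real, although it shows no bias in the interaction estimate. What does not follow is that the plan is wrong or that one particular repair is better. Limiting the primary model to chart variables keeps every patient but measures depression and anxiety more coarsely. In a non-randomised comparison that could weaken adjustment for shifts in case mix over time. Imputing the survey scores or using a missing-data indicator keeps every patient as well, with different weaknesses. The choice is a trade-off that the analyst can make once the extent of missing data is known. The subgroup wording adds little, since a subgroup by a measured characteristic uses the patients in whom it was measured and leaves the main model intact.

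**Conclusion.** The concern does not call for a change. Section 10 leaves a detail open, namely which covariates from which source enter the primary models and what happens when they are missing. An analyst who sees unreached patients vanish from a records-based analysis would use chart covariates or impute, and both fit the text.

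The possible loss cannot be determined from the documents. If all 129 have baseline data, it runs from 0 to 69 of 198 (35%, standard error up to 1.24 times larger). It reaches 82 of 198 (41%, factor 1.31) only by adding an assumed 10% baseline non-completion. Every non-zero figure depends on survey-measured covariates in the primary model and on dropping incomplete records, and the upper ends also need no non-consenter to have declined. The effect would be on coverage and precision; bias is not shown. The plan gives no alpha, power or target effect, so no loss of power can be stated.

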1 BACKGROUND/SCIENTIFIC RATIONALE

- Prescription opioid use by adolescents and young adults aged 12-25 years increases their risk of prescription opioid misuse.^{1,2} Leftover opioids from prior prescriptions for acute pain are a key driver of this misuse. As such, it is crucial to ensure that quantities in opioid prescriptions match the needs of adolescents and young adults.³
- Several prior studies have utilized default dosing settings to reduce the size of opioid prescriptions written to adults. In a study in the University of Pennsylvania adult emergency department, the default quantity of oxycodone-acetaminophen tablets in the electronic health record (EHR), was set to 10 tablet; providers could override the settings and prescribe other quantities at their discretion. After this intervention was implemented, the percentage of Percocet prescriptions written for 10 tablets increased from 20.6% to 43.3%, demonstrating that EHR default settings can affect opioid prescribing.⁴
- However, no study has utilized default dosing settings to promote appropriate opioid prescribing to adolescents and young adults. Furthermore, no study of default dosing settings to date has chosen the level of these settings based on evidence on patient need.
- In this study, we will collect data on patient-reported post-surgical opioid consumption among adolescents and young adults undergoing tonsillectomy at the University of Michigan. These data will inform the design of a default dosing setting intervention. We will assess whether implementation of the intervention is associated with changes in opioid prescribing and consumption. Additionally, we will assess for potential unintended consequences, including worsened patient satisfaction, pain control, sleep, anxiety, depression, and functioning; or increased requests for refills or return visits for uncontrolled pain.
- The research team has significant experience with collecting data on patient-reported opioid consumption and patient-reported outcomes such as pain control, as well as with developing evidence-based opioid prescribing guidelines.

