10 STATISTICAL CONSIDERATIONS

- Outcomes in primary analysis
 - Number of doses in the discharge opioid prescription
 - Proportion of patients in which the number of doses in the discharge opioid prescription equals the number of doses in the new default settings
 - Proportion of patients prescribed opioids at discharge
 - Proportion of patients prescribed opioids at discharge who had at least one opioid prescription refill from UM during the two weeks after surgery
 - Proportion of patients who saw a UM provider in an office due to pain during the two weeks after surgery

- Proportion of patients with at least one emergency department visit or hospitalization at UM for pain during the two weeks after surgery
- Additional outcomes in secondary analysis (based on data from the final post-operative day 14 survey)
 - Overall satisfaction with pain control during the two weeks after surgery (scale of 1-10)
 - Proportion of patients who reported that their pain was well-controlled
 - Proportion of patients whose overall pain control was rated as much worse or worse than expected
 - Proportion of patients whose pain has resolved by day 14 after surgery
 - Pain score over the past 7 days at its worst (scale of 0-10)
 - Pain score over the past 7 days on average (scale of 0-10)
 - Number of opioid doses taken during the two weeks after surgery
 - Proportion of patients with leftover doses of opioids
 - Proportion of patients with leftover doses who disposed of them
 - Proportion of patients who misused opioids belonging to others at least once during the two weeks after surgery
 - Proportion of patients who misused their own opioids at least once during the two weeks after surgery
 - PHQ-8 score (depression)
 - Score on PROMIS Pediatric Anxiety – Short Form 8a
 - Score on PROMIS Sleep Disturbance – Short Form 8a
 - Proportion of patients who saw their primary care provider (or a colleague) in the office due to poorly controlled pain at least once during the two weeks after surgery
 - Proportion of patients who visited an urgent care center due to poorly controlled pain at least once during the two weeks after surgery
 - Proportion of patients who visited a retail clinic due to poorly controlled pain at least once during the two weeks after surgery
 - Proportion of patients who went to an emergency department and/or were hospitalized due to poorly controlled pain at least once during the two weeks after surgery

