- Sample size: Based on historical UM data, we estimate that there will be 113 patients in the treatment group and 85 in the control group for the primary analysis (total 198). If 65% consent to complete the surveys, then there will be 74 and 55 patients in the treatment and control groups for the secondary analysis, respectively (total 129).

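### Does the hypothesis of no change in balancing measures need a margin or decision rule in the plan?

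*Combined protocol and SAP*

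**What the plan says.** Section 1 of the combined protocol and SAP sets the aim: "we will assess for potential unintended consequences, including worsened patient satisfaction, pain control, sleep, anxiety, depression, and functioning". The same sentence adds refill requests and repeat visits because of pain. Section 10 turns this into outcomes. Some come from the medical record and sit in the primary analysis: opioid refills, office visits for pain, and "Proportion of patients with at least one emergency department visit or hospitalization at UM for pain during the two weeks after surgery". The others come from the day-14 survey and sit in the secondary analysis.

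All outcomes share one main model, a linear or logistic regression on "an indicator of post-intervention status, an indicator of treatment group status, and its interaction", with adjustment for demographics and baseline comorbidities. For the balancing measures the stated expectation is "and that there will be no change in balancing measures such as pain control or depression".

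The sample size item in Section 10 gives expected counts only. For the record-based outcomes, "we estimate that there will be 113 patients in the treatment group and 85 in the control group for the primary analysis (total 198"; at 65% consent, "then there will be 74 and 55 patients in the treatment and control groups for the secondary analysis, respectively (total 129". No power, detectable difference, significance level or margin is stated for any outcome. Section 4 also removes from the survey analysis "Patients who do not complete the baseline and post-operative day 14 surveys".

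**The concern.** The hypotheses on prescribing and consumption predict a difference, and an interaction term is suited to showing one. The hypothesis on balancing measures predicts the absence of a difference, and the same interaction term does not show that by failing to reach significance. With modest numbers, a null result can sit beside a worsening that patients would notice.

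Nothing elsewhere in the document supplies a criterion. Section 10 explains no change only for the control group, as a continuation of its earlier trend. The stopping rule in Section 11.3 speaks of substantially higher rates without a number, and it concerns stopping, not interpretation. The plan to contact the surgical team when a patient reports poor pain control is individual follow-up.

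At stake is the conclusion on unintended consequences, which readers will want because Section 3 foresees wide adoption. The conclusion on prescribing is not touched.

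**Working it through.** **The plan's own figure.** 113 + 85 = 198. At 65% consent: 113 × 0.65 = 73.45, 85 × 0.65 = 55.25 and 198 × 0.65 = 128.7. The plan prints 74, 55 and 129. The counts therefore reproduce to within one patient of rounding.

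**Assumptions not in the documents.** Two-sided 5% level; independent patients; normal approximation; counts cover both periods. The Section 6 timeline leaves 10 months before the change (12 less April and May 2020) and 10 after, so an even split is reasonable.

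**Continuous survey scores (74/55), unadjusted.**
- SE in SD units = √(4/74 + 4/55) = √(0.0541 + 0.0727) = 0.356.
- 95% half-width = 1.96 × 0.356 = 0.70 SD. On a 0–10 pain score with an assumed SD of 2 to 3, that is 1.4 to 2.1 points.
- Power against a 0.5 SD worsening: 0.5/0.356 = 1.404, and Φ(1.404 − 1.96) plus a negligible lower tail = 29%. Against 0.8 SD: 61%.
- A non-significant result despite a true 0.5 SD worsening: 100 − 29 = 71% of trials.

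**How far that moves.** The planned model adjusts for covariates, the survey set loses non-completers, and the sample size item does not say whether its counts cover one period or both.

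| Scenario (survey scores) | Half-width, SD | Power at 0.5 SD |
|---|---|---|
| Both periods, 80% completion (59.2/44), unadjusted | 0.78 | 24% |
| Both periods, unadjusted | 0.70 | 29% |
| Both periods, covariate R² = 0.3 | 0.58 | 39% |
| Both periods, covariate R² = 0.5 | 0.49 | 51% |
| Counts per period, unadjusted: SE = √(2/74 + 2/55) = 0.252 | 0.49 | 51% |
| Counts per period, R² = 0.3 | 0.41 | 66% |
| Counts per period, R² = 0.5 | 0.35 | 80% |

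Adjusted rows multiply the SE by √(1 − R²). Clustering by clinician is left out and would probably widen the intervals.

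**What the SD scale covers.** In the Section 10 survey list, six balancing measures are scores (satisfaction, two pain scores, PHQ-8, anxiety, sleep). Nine are proportions: three on pain control or resolution, two on misuse, four on visits. All three record-based measures are proportions too, so the figures above describe a minority of the balancing measures.

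**Record-based proportions (113/85).** The half-width on the linear scale is 1.96 × √(p(1 − p)(4/113 + 4/85)). At an assumed rate of 5% it is 12 percentage points, and at 10% it is 17.

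At a 10% rate the SD is √(0.1 × 0.9) = 0.3, so 0.5 SD is a rise to 25%. The normal-outcome formula would give 41% power for this, which is too high because the variance grows with the rate. With cells of 57/56 treated and 43/42 control:
- SE = √(0.09/57 + 0.1875/56 + 0.09/43 + 0.09/42) = 0.0957.
- 0.15/0.0957 = 1.567, so power = Φ(1.567 − 1.96) = 35%. Simulation gives 33% to 36%, depending on the variance estimate used.

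**What a margin would buy.** For a survey score with no true effect, the 95% interval would exclude a 0.5 SD worsening with probability Φ(0.5/0.356 − 1.96) = 29%. For 80% power at that margin (one-sided 2.5%), with allocation a = 74/129:

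N = (4/a + 4/(1 − a)) × ((1.96 + 0.842)/0.5)² = (6.97 + 9.38) × 31.4 ≈ 514.

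The plan expects 129, already recruits every eligible patient, and takes its numbers from surgical volume.

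**The case for a change.** The strongest case for acting is that a stated hypothesis needs some basis for judging it, and that this one concerns harm. Section 3 says earlier studies did not evaluate depression, suicidal ideation or misuse, so this study may be cited on those points. A sentence asking for intervals, and barring any inference from non-significance alone, would cost no patients and no data.

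Part of this stands. The document contains no criterion, and a null interaction read alone would be weak evidence. The advice is also sound reporting practice.

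It does not show a fault in the plan, for three reasons. First, Section 10 says which models will be fitted. It does not name a test of the balancing hypothesis, a p-value rule, or a reading of non-significance as no change, so the harm is a misreading that has not been written down. Second, the fitted interaction term gives the difference-in-differences estimate and its interval without any amendment. Third, a sentence asking authors to call a result inconclusive when a material worsening is not excluded leaves material undefined, so it does not supply the missing criterion. A margin would supply one, but at the expected size it would usually fail even with no harm at all.

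**Conclusion.** No change is needed. The plan leaves a matter of interpretation to the analysts, and the planned model gives them what they need to handle it: an estimate and interval for each balancing measure. No figure or rule in the plan is wrong, and the plan promises no power that the design misses.

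The limit on precision is real and should be kept in mind when results are read. It is about ±0.70 SD for a continuous survey score, if the counts cover both periods, split evenly and unadjusted. It is about ±12 to 17 percentage points for record-based proportions at assumed rates of 5% to 10%. The first figure could be as small as 0.35 SD under the per-period reading with strong covariates, or as large as 0.78 SD with 80% survey completion. R², completion, event rates and the 5% level are assumptions. The lack of a written criterion does not depend on them, but that lack alone is missing detail rather than an error.
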